11.4 Completion Flags

Subjects who completed the study will be flagged in analysis datasets.

11.5 Study Duration and Treatment Duration

Study duration of VR intervention participation to the study is defined as:

- Study Duration of VR intervention participation (days) = (Date/time of Last Visit – Date/time of Informed Consent) + 1.
- Study Duration of VR intervention participation (weeks) = ((Date/time of Last Visit – Date/time of Informed Consent) + 1) / 7.

Treatment duration of VR intervention participation to the study is defined as:

- Treatment duration of VR intervention participation (days) = (Date/time of last required VR session – Date/time of first required VR session) + 1.
- Treatment duration of VR intervention participation (weeks) = ((Date/time of last required VR session – Date/time of first required VR session) + 1) / 7.

11.6 Discontinued Subjects

Discontinued subjects will have assessments at the ET visit within 5 days of the last exposure to the investigational intervention and will be summarized along with Visit 7 Week 8.

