#### **11.5.6. Early Termination**

For subjects who prematurely discontinue from the study, every effort should be made to complete the final evaluation procedures, as described in [Section 11.5.4](#) and including clinical and PRO assessments , as well as the Qualitative Interview outlined in [Section 11.3.7](#) at the ET visit. This ET visit should occur within 5 days of the last exposure to the Investigational Intervention, including the qualitative interview and PROs if they have not been completed by the subject for the given week.

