9.1 Handling Missing/Incomplete Data

9.1.1 Missing Data in Efficacy Analysis

Missing data will not be imputed for efficacy endpoints analyses.

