10.5 Per-Protocol Population

The Per-Protocol population consists of all ITT subjects who have completed the 8-week intervention period without any important protocol deviations.

The PP population is the population used for supportive analysis of the primary endpoint. Demographic and baseline characteristics of the PP population will be presented. Subjects will be analyzed according to the treatment they received.

11 Analysis Variables

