11.3 Analysis Visits

All analysis datasets with measurements taken at more than one visit/time point will have analysis visit and timepoint as defined below.

Collected Visit	Analysis Visit
Screening	Visit 1 Screening
Randomization	Visit 2 Randomization
Week 1	Visit 3 Week 1
Week 2	Visit 4 Week 2
Week 4	Visit 5 Week 4
Week 6	Visit 6 Week 6
Week 8/ End of Study/ Early Termination	Visit 7 Week 8

A subject is considered to have attended any visit only if at least one assessment has been taken at the visit. As per section 11.10, derived baseline results will also be presented in summary tables.

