11.17.8 Responder Rate

Responder rate based on the CGI-I score is the proportion of responders at Week 8. Responders are subjects who rated 1 (very much improvement) or 2 (much improvement) in CGI-I at Week 8.

$$\text{Responder Rate} = \frac{\text{Number of responders at Week 8 in a treatment group}}{\text{Total number of subjects in that treatment group in mITT}}$$

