12.8 Efficacy Analyses

12.8.1 Primary Efficacy Analysis

12.8.1.1 Descriptive Summaries

The following summaries will be presented by treatment groups based on ITT and PP population. For Credibility, Expectancy, Total CEQ Score separately, descriptive summary of observed and change from baseline results for expectancy and credibility score will be summarized by visit (Baseline, Week 6 and Week 8/EOS). Also, descriptive summary of the total CEQ score and score for each item will be summarized based on treatment groups and visit. Mean Credibility and Expectancy scores will be plotted using line plots by visit. All listings are based on enrolled population.

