12.9 Exploratory Analyses

12.9.1 Descriptive summaries

Descriptive summary of change from baseline results for total LSAS score and subscores, CGI-S score and PHQ-9 score, and the observed scores will be summarized by treatment groups and week based on ITT population. Observed scores for CGI-I score and PGI-I score will be summarized by treatment groups and week based on ITT population. Descriptive summary of the number of required sessions completed during the study will be summarized by treatment groups based on ITT population. All scores will be listed based on all Enrolled Population

For LSAS summary parameters to be summarized are: LSAS Total Score, Fear of performance situations, Avoidance of performance situations, Fear of social interaction, Avoidance of social interaction, Total fear and Total avoidance. Average of LSAS score will be plotted using line plot by treatment group and week. All listings are based on the Enrolled Population.

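### Early-termination assessments are reported as Week 8 whatever day they were made, so ITT Week 8 results mix 8-week and earlier outcomes

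*SAP*

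**What the plan says.** The visit table in SAP 11.3 has one collected visit, "Week 8/ End of Study/ Early Termination", and assigns it to Visit 7 Week 8. SAP 11.6 repeats the rule for discontinued subjects: their ET assessments fall under "intervention and will be summarized along with Visit 7 Week 8". The Week 8 visit is scheduled for Days 50-56 (SAP 4.1 and 5). ET is timed from the last use of the device. Protocol 11.5.6 says: "This ET visit should occur within 5 days of the last exposure to the Investigational Intervention".

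ITT (SAP 10.4) keeps every randomised subject with at least one VR session, so it includes early leavers. The per-protocol set does not (SAP 10.5): "The Per-Protocol population consists of all ITT subjects who have completed the 8-week intervention period without any important protocol deviations". CEQ is shown on both sets (SAP 12.8.1.1): "The following summaries will be presented by treatment groups based on ITT and PP population". The exploratory scales are shown on one (SAP 12.9.1): "PHQ-9 score, and the observed scores will be summarized by treatment groups and week based on ITT population".

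Two linked rules matter here. The responder formula in SAP 11.17.8 divides by "Total number of subjects in that treatment group in mITT", although SAP 13 removes that population. SAP 11.11 counts Study Day only from the first BVR-100 session, which leaves it undefined for the BES-100 arm.

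**The concern.** Week 8 is a time point of the primary CEQ endpoint and the time point of the responder rate. The protocol also says the LSAS and CGI results are collected to match endpoints of the later RCT. A column headed Week 8 should describe subjects after about eight weeks. Under this mapping it can also hold ratings made after one or two weeks of use, and the share of such ratings can differ between arms if attrition or ET attendance differs. The SAP then tests between-arm differences on these values: a t-test or Mann-Whitney test for CEQ and LSAS, and Fisher's exact test for responders. For the exploratory scales no planned result shows what the Week 8 figure would be without the early values.

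**Working it through.** **1. The plan's own figure.** Inputs: 15 per arm and 25% attrition (SAP 4.2, Protocol 15.1). 15 / (1 - 0.25) = 20 per arm, and 2 x 20 = 40 in total, which matches. The plan thus allows for 20 - 15 = 5 leavers per arm.

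**2. Timing.** Inputs: ET within 5 days of last exposure; Week 8 opens on Day 50.
- Last session on Day 14: ET by Day 14 + 5 = 19, which is 50 - 19 = 31 days before the window.
- Last session on Day 1: ET by Day 1 + 5 = 6, which is 50 - 6 = 44 days before it.

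The 5 days are a target, not a hard limit, so these are examples. Short exposure is foreseen: the duration categories in SAP 12.7 begin at 0 to 2 weeks.

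**3. Where ET values land.**

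| Week 8 result | Population | ET values included? |
|---|---|---|
| CEQ summary and test | ITT | Yes |
| CEQ supportive summary and test | Per-protocol | No |
| LSAS, CGI-S, CGI-I, PGI-I, PHQ-9 | ITT only | Yes |
| CGI-I responder rate | ITT (formula says mITT) | Yes |

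Summaries at Weeks 2, 4 and 6 carry no ET data under this mapping. Time-on-task is recorded by the device per session and is not affected.

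**4. Share of the Week 8 rows.** With 15 completers per arm and k leavers attending ET, the share is k / (15 + k):
- k = 0: 0%
- k = 1: 1/16 = 6.3%
- k = 2: 2/17 = 11.8%
- k = 3: 3/18 = 16.7%
- k = 4: 4/19 = 21.1%
- k = 5: 5/20 = 25%

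In general, with attrition d and attendance e, the share is d x e / (1 - d + d x e). If all leavers attend, it equals d, so the upper end is 10% at 10% attrition and 40% at 40%. The formula assumes that every completer has a Week 8 value. It cannot be used for CEQ: SAP 13 reports that at the January 2024 data cutoff only 24 of 52 subjects (46%) met the mITT definition, because CEQ data were missing.

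**5. Responder rate.** Each ET rating of 1 or 2 adds 1/20 = 5.0 points with 20 per arm, or 1/26 = 3.8 points if the 52 subjects in SAP 13 are split evenly (an assumption).

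**6. How an imbalance could act (illustration only).** Assume the same linear change C over 8 weeks in both arms, attrition of 10% and 40%, and ET at Week 2 for every leaver. The pooled Week 8 means are 0.90C + 0.10C x 2/8 = 0.925C and 0.60C + 0.40C x 2/8 = 0.700C. That is a gap of 0.225C with no true difference. With ET at Week 6 the gap is 0.975C - 0.900C = 0.075C. None of these inputs is in the documents.

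**The case against.** The pooling is open and prespecified. The schedules in both documents show one combined W8/EOS/ET visit, and the primary time point is worded as Week 8/EOS. This is a pilot for which Protocol 15.4.2 plans no formal hypothesis testing. The mixture can also be traced: SAP 12.1 reports completers and early terminations with reasons, SAP 12.7 tabulates treatment duration by arm, and listings show all recorded data by subject and date.

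Most of this stands, and it limits the weight of the point. But a combined visit for scheduling does not require one undivided summary row. The exploratory endpoints in SAP 7.4 are named Week 8 alone. Being able to rebuild the mixture from listings is not the same as having a Week 8 result without ET data.

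Three stronger readings are tempting, and the documents do not support them:
- A reader might infer that the pooling breaks SAP 9.1.1, "Missing data will not be imputed for efficacy endpoints analyses". It does not. An ET rating is an observed value placed under a visit label; nothing is filled in.
- A reader might infer that an ET attendee counts as retained at Week 8, from the shared label, the Week 6 note in SAP 11.17.2 and the broad EOS definition in SAP 2. But SAP 7.2 speaks of subjects remaining on the study, Protocol 4.3 equates retention with drop-out, and Protocol Table 4 defines an early-termination subject as one who did not complete. This is at most a gap in wording.
- A reader might infer that the responder rate will really be divided by the smaller mITT set. SAP 13 removes that set and the appendix assigns the responder rate to ITT, so the word is a leftover.

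The Study Day rule also looks like a slip, since SAP 11.14 names both interventions. No analysis described in the SAP uses Study Day, but it is the natural variable for reporting when ET visits took place.

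**Conclusion.** The point holds and should be fixed before the tables are run, though it does not undermine the pilot. As written, ITT Week 8 means, p-values and the responder rate combine 8-week outcomes with any earlier ET outcomes, and the per-protocol CEQ analysis is the only visit-based Week 8 result without them. That analysis also drops subjects with important protocol deviations, so it does not isolate the effect of the ET data.

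The size is 0% to 25% of Week 8 rows per arm, given 20 per arm, 25% attrition and complete completer data, with ET attendance anywhere from none to all. The share for CEQ cannot be stated. The documents give neither the number nor the timing of ET visits, so no direction or amount of bias can be claimed.

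**What to change.** 1. In SAP 11.3 and 11.6, give ET its own analysis visit. For each ITT endpoint, show Week 8 for subjects who reached the Week 8 visit, late completers included, next to a pooled row labelled Week 8/ET. State which row takes an ET assessment that happens to fall in Days 50-56. The pooled row keeps the sparse CEQ data.
2. In SAP 11.17.8, replace mITT with ITT, in line with SAP 13 and the appendix. Report the responder rate with ET ratings included and, separately, among subjects with a Week 8 rating. If all ITT subjects are the denominator and ET ratings are left out, say that dropouts then count as non-responders.
3. In SAP 11.11, count Study Day from the first session of either intervention.
4. Optional: add a line to SAP 11.17.2 saying that an ET visit does not count as remaining on the study at Week 8 and does not trigger the Week 6 note.

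The cost is SAP wording and a little programming; the completion flag in SAP 11.4 already identifies completers, and no new data are needed. The ET-free row will have a smaller n and describes only subjects who stayed, so it is not a bias-free estimate either. Showing both rows lets the reader see how far the Week 8 result depends on the early values.

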11.7 Replacement Subjects

Additional subjects may be enrolled as replacement to early discontinuation subjects into the study to ensure adequate data for evaluation. For such subjects, summaries will include data like any other subjects.

11.8 Rescreened Subjects

Subjects who fail screening may be rescreened into the study if they meet the eligibility criteria. For such subjects, summaries will include the latest data reported.

11.9 Common Derivations

The following variables will be derived in analyses datasets and used in summaries as per the formula below:

- Age (years) = Year of Informed consent – Year of Birth

These variables will be derived and verified against EDC calculated values. In cases where they do not match, queries will be raised. If not reconciled until database lock, derived values will be considered correct and will be used in TLFs.

11.10 Baseline

Baseline is defined as the latest non-missing measurement prior to first video-guided VR onboarding session on week 1 day 1 including repeat assessments and unscheduled visits.

For CEQ scores, baseline is defined as first non-missing measurement taken after the first self-guided VR session and before week 1 day 7.

11.10.1 Change from Baseline

Change between baseline and post-baseline result will be calculated as below.

- Change = Result at Visit X – Baseline Result

11.11 Study Day

Study Day 1 will be the day the first BVR-100 session. Study Day will be calculated as:

For events that occurred on the day of or after first BVR-100 session:

- Study Day = visit date – date of first BVR-100 session +1

For events that occurred on the day before first BVR-100 session:

- Study Day = visit date – date of first BVR-100 session

11.12 Protocol Deviations

Protocol deviations will be classified as Important and Non-Important. Important protocol deviations will be used for summarization.

11.13 Medical / Psychiatric History

If a condition has end date prior to first exposure to the investigative intervention or if the Ongoing status = No, then these will be flagged as Medical / Psychiatric History.

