## 8. SELECTION OF SUBJECTS

### 8.1. Subject Inclusion Criteria

To qualify for participation, subjects must meet all the following inclusion criteria:

1. Subject has provided written informed consent, obtained prior to initiation of any study-specific procedures.
2. Subject is male or female, aged 18 or above.
3. Subject has English fluency and literacy, sufficient to provide consent and follow study instructions as judged by the Investigator.
4. Subject meets the Diagnostic and Statistical Manual of Mental Disorders, Fifth Edition, (DSM-5) criteria for Social Anxiety Disorder as established during the Screening visit using the MINI. Subjects may have a comorbid DSM-5 based diagnosis of generalized anxiety disorder and/or a comorbid DSM-5 based diagnosis of specific phobias provided the symptoms of the comorbid disorder(s) are secondary to symptoms of SAD and are considered stable during the 3 months prior to Screening, in the opinion of the Investigator.
5. Subject has a total Liebowitz Social Anxiety Scale (LSAS) score at Screening of  $\geq 70$ .

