### 8.2. Subject Exclusion Criteria

Subjects who meet any of the following criteria will not be eligible to participate in the study:

1. Subject has significant visual, auditory or balance impairment (eg, vertigo, stereoscopic visual impairment).
2. Subject has history of photosensitive epilepsy, seizure disorder or other disorders that may negatively affect the subject's ability to engage with VR and/or their safety.
3. Subject has cognitive, reading or learning disabilities that prevent the comprehension of instructions or is likely to interfere in the subject's ability to engage with the investigational intervention, based on the opinion of the Investigator.
4. Subject has history of motion sickness or medical condition predisposing to nausea or dizziness that is likely to interfere in the subject's ability to engage with the investigational intervention, based on the opinion of the Investigator.
5. Subject has injuries, inflammation or infection affecting the eyes, ears or face that would make the use of the hardware uncomfortable.
6. Subject has, as judged by the Investigator based on intake interview and subject report, current or lifetime history of meeting DSM-5 criteria for schizophrenia spectrum or other psychotic disorder, bipolar or related disorder, major neurocognitive disorder, neurodevelopmental disorder of greater than mild severity or of a severity that impacts the subject's ability to consent, follow study directions, or otherwise safely participate in the study; posttraumatic stress disorder, major depressive disorder (MDD) with psychotic features, Borderline or antisocial personality disorder, or any other current comorbid psychiatric disorder that either would be likely to require treatment with prohibited

concomitant medications or psychotherapy during this trial, or to confound effectiveness or safety assessments. Prior history of panic disorder or obsessive-compulsive disorder may be acceptable provided subject no longer meets DSM-5 criteria for these disorders. Prior history of MDD (without psychotic features) may be acceptable provided the subject does not currently meet DSM-5 criteria for a major depressive episode.

7. Subject has met DSM-5-based criteria for Alcohol or Substance Use Disorder (other than nicotine or caffeine) within one (1) year prior to Screening based on MINI and opinion of the Investigator.

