## **15.4. Demographic and Baseline Characteristics**

All analyses will be based on mITT population as described in [Section 15.2](#), as well as a secondary analysis of the PP and Safety populations.

Baseline demographic and clinical characteristics will be presented descriptively as proportions or as means with standard deviations. Baseline demographic and clinical characteristics will be compared between groups with the use of the two-sample *t*-test and the Mann–Whitney test for continuous measurements with and without normal distribution, respectively.

Medical history will be coded using the Medical Dictionary for Regulatory Activities (MedDRA) version 26.0 or higher and will be summarized for the safety population by presenting the number and percentage of subjects with at least one condition in each system organ class (SOC) and preferred term (PT).

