12.4 Psychiatric and Medical History

Number and percentage of subjects with any psychiatric or medical history and number of events will be summarized by treatment groups and total based on safety population. The same will be classified by System Organ Class (SOC) and Preferred Term (PT). The SOC and PT will be displayed in the descending order of frequency in “Total”. Medical history will be coded using the Medical Dictionary for Regulatory Activities (MedDRA) version 26.0 or Higher.

The summary will be presented by following categories:

- Comorbid psychiatric conditions
- General Medical History separately

Above analysis details are specified in DDP Table 14.1.5.1.

Psychiatric details collected for subject who are screened will be listed in DDP Listing 16.2.4.2.1

Psychiatric and Medical History will be listed by subject and body system based on Safety Population. List details are specified in DDP: Listing 16.2.4.2.2

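### The SAP's definition of Medical / Psychiatric History never captures an ongoing condition, so a comorbidity table built from it would omit the current anxiety disorders that the protocol admits

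*SAP*

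**What the plan says.** SAP 11.13 sets a two-limb test, "If a condition has end date prior to first exposure to the investigative intervention or if the Ongoing status = No", and conditions that pass it are classed as history: "then these will be flagged as Medical / Psychiatric History". Nothing in that section deals with a condition that is still present.

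SAP 12.4 describes the table that reports history, on the Safety Population: "Number and percentage of subjects with any psychiatric or medical history and number of events will be summarized by treatment groups and total". One of its two parts is headed "Comorbid psychiatric conditions"; the other is general medical history. The table is numbered 14.1.5.1 in the Data Display Plan.

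Inclusion criterion 4 (Protocol 8.1) states "Subjects may have a comorbid DSM-5 based diagnosis of generalized anxiety disorder and/or a comorbid DSM-5 based diagnosis of specific phobias", provided that the comorbid symptoms are secondary to social anxiety disorder and "are considered stable during the 3 months prior to Screening". Exclusion criterion 6 (Protocol 8.2) treats some other disorders differently: "Prior history of panic disorder or obsessive-compulsive disorder may be acceptable provided subject no longer meets DSM-5 criteria for these disorders".

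Protocol 15.4 plans the medical history summary as the "number and percentage of subjects with at least one condition in each system organ class (SOC) and preferred term (PT"), with no restriction to conditions that have ended. SAP section 13, which lists departures from the protocol, has no entry on this point.

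**The concern.** A history table in a trial report is normally expected to show what subjects brought with them into the study, current problems included. The SAP's rule selects on whether a condition is over. The psychiatric comorbidities that the protocol expressly allows at entry are current disorders, so they would normally be recorded as ongoing and would fall outside the definition. Past disorders would fall inside it.

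The stake is descriptive but real. The baseline clinical characteristics in SAP 12.3 are CEQ, credibility, expectancy, LSAS, CGI-S and PHQ-9; comorbid diagnoses are not among them. Table 14.1.5.1 is therefore the only planned summary in which a reader could see whether comorbid anxiety is similar in the two arms. Protocol 4.3 and 7.3.1 say that this pilot is to inform a later trial with broadly the same entry criteria, so an accurate account of who was enrolled is part of its purpose.

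**Working it through.** The plan gives no figure here to reproduce. The check is a truth table for the rule in SAP 11.13, applied to the kinds of condition that the protocol allows.

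**Inputs.** The two limbs of SAP 11.13; the table in SAP 12.4; inclusion criterion 4 and exclusion criterion 6; Protocol 15.4; SAP 11.14 for comparison; SAP section 2 for precedence.

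**Step 1: the rule.**

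| Case | End date | Ongoing | Limb 1 (ended before first exposure) | Limb 2 (Ongoing = No) | Flagged |
|---|---|---|---|---|---|
| a | Before first exposure | No | Met | Met | Yes |
| b | On or after first exposure | No | Not met | Met | Yes |
| c | None recorded | No | Not met | Met | Yes |
| d | None recorded | Yes | Not met | Not met | **No** |

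Every flagged case is a condition recorded as over. Every ongoing condition falls in case d.

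**Step 2: apply it to the conditions that the protocol allows.**

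- Stable comorbid generalized anxiety disorder or specific phobia, still present: case d, not flagged.
- A chronic medical condition under stable treatment, which Protocol 10.3 anticipates: case d, not flagged.
- Past panic disorder or obsessive-compulsive disorder, now resolved: case a, or c if the end date is missing; flagged.

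**Step 3: look for another rule that picks up case d.** SAP 11.14, the next section, gives ongoing medications a class of their own (concomitant). No section does the same for conditions, and 11.13 is the only place in the SAP that defines Medical / Psychiatric History.

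**Step 4: compare with the protocol.** Protocol 15.4 counts subjects with one or more conditions per term, so case d would be counted. SAP section 2 says that the SAP prevails over the protocol's statistical section where the two differ, so the narrower SAP rule would govern.

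**Step 5: size.** If the table uses the flag, all ongoing pre-study conditions are missing from it. The number of subjects this affects cannot be derived, because the documents give no comorbidity rate. SAP section 13 puts the Safety Population at 52. If between 20% and 50% of them had ongoing generalized anxiety disorder or a phobia (an assumed range), the count would run from 0.20 × 52 = 10.4, about 10, to 0.50 × 52 = 26. These figures only restate the assumption.

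**The case against.** The strongest answer is that SAP 12.4 never mentions the flag, end dates or ongoing status. Its heading for comorbid conditions ordinarily means disorders that are present now. A programmer might use 11.13 only to separate past from current conditions, much as 11.14 separates prior from concomitant medications, and report current disorders under that heading. The table shell is in the Data Display Plan, which is not among the documents. Protocol 15.4 has no restriction and section 13 announces none, which suggests that none was intended.

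This stands as a limit on certainty. A reader might infer that Table 14.1.5.1 is bound to omit every ongoing condition, or that it will show the reverse of comorbidity. The documents do not establish either; both hold only if the table is built from the 11.13 definition. The objection does not rescue the text, though. A programmer following the SAP has one definition to work from, and it excludes ongoing conditions.

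Three further points stand:

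- The data are not lost. SAP 12.4 plans Listing 16.2.4.2.1 of psychiatric details for screened subjects, described without reference to the flag, and Listing 16.2.4.2.2 of psychiatric and medical history. Listing 16.2.4.2.2 might carry the same restriction. A listing allows a hand count but does not replace a by-arm summary.
- A reader might also take case b, a condition that ended after first exposure, as wrongly flagged. It is not: if it began before the study, it belongs in history.
- The weight of comorbid anxiety is limited by criterion 4 itself, which requires it to be secondary to social anxiety disorder and stable.

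**Conclusion.** The concern holds as a defect in a stated definition with a conditional consequence. On its plain wording, SAP 11.13 leaves ongoing pre-study conditions out of Medical / Psychiatric History and assigns them nowhere else. This conflicts with Protocol 15.4 without being declared. If Table 14.1.5.1 follows that definition, the comorbidity summary omits the current disorders allowed by criterion 4 and keeps the resolved ones.

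Two assumptions carry the consequence: that the table is built from the SAP's only definition, and that comorbid disorders present at entry are recorded as ongoing. A comorbid disorder that was active at first exposure but later closed with Ongoing = No would still be counted.

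The effect stops at the description of the sample and the reading of balance between arms. It would be wrong to infer any bias in the study's results: no analysis of CEQ, retention, time-on-task, LSAS, responder status or adverse events uses this flag. The correction is worth making because the rule gives the wrong content for a planned table and is cheap to repair.

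**What to change.** Change SAP 11.13 so that Medical / Psychiatric History is any condition with onset before informed consent, or recorded on the history form at Screening, whatever its ongoing status.

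The cut-off should be consent, not the first VR session. Protocol 12.1.1 and 15.4.3 and SAP 11.15 already class occurrences between consent and the first session as pre-treatment events, and a first-session cut-off would count them as history too. State that they remain pre-treatment events.

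In SAP 12.4, say that Table 14.1.5.1 includes both ongoing and resolved conditions, shown by status, with ongoing psychiatric disorders under the comorbid heading. Check that the Data Display Plan shell and Listing 16.2.4.2.2 follow the same rule.

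The cost is a sentence in each of the two sections and one change to a derivation. No new data are needed: 11.13 already relies on the end date and ongoing status, and if onset dates are incomplete, entry on the Screening form is enough.
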